## **Rollover Subjects**

- The first dose of open-label brexpiprazole (OPC-34712) will be taken one day after the last dose of double-blind IMP is taken in Trials 331-201-00080 or 331-201-00081 so that treatment continues without interruption. It is anticipated that the last dose of the double-blind, phase 3 efficacy trial will be taken the day of the Day 21 (Week 3) visit of Trial 331-201-00080 or 331-201-00081 (ie, the day of the screening/baseline visit for the open-label trial).
- All subjects will start on 2 mg/day of brexpiprazole (OPC- 34712) regardless of treatment assignment in the double-blind trial.

All subjects will receive a starting dose of 2 mg/day of brexpiprazole from Days 1 to 3, followed by titration to 3 mg/day brexpiprazole on Day 4. Subjects may be titrated (or re-titrated) to a higher dose of brexpiprazole, up to a maximum of 4 mg/day, based on treatment response and at the investigator's discretion anytime at Day 7 or thereafter. Subjects who are unable to tolerate their current dose can be titrated down at any time to a minimum of 2 mg/day. Dose adjustments must be made in increments of 1 mg/day.

Confidential - Proprietary Information

Subjects who are unable to tolerate 2 mg/day brexpiprazole will be discontinued from the trial.

The dosing strategy is summarized in Table 3.2.2.1-1. Subjects must return to the clinic for unscheduled visits if dose adjustments for brexpiprazole are required between scheduled visits. Dose adjustments must ultimately be made based upon the clinical judgment of the investigator as it relates to tolerability and therapeutic response. All doses of brexpiprazole should be taken orally once daily and can be administered without regard to meals. Subjects are to take IMP at approximately the same time each day.

Table 3.2.2.1-1 Dosing Schedule - Open-label Treatment Phase						
		Trial Visit				
IMP	Days 1-3	Day 4 a	Day 7-Week 26			
Brexpiprazole (OPC-34712)	2 mg/day	3 mg/day	2-4 mg/day b			

<sup>aDown titration can occur at any time due to tolerability after Day 4. The minimum dose allowed is 2 mg/day.

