
 
Subjects with abnormal laboratory tests results, vital signs results, or ECG findings, unless, on the investigator's judgment, the findings are not medically significant and would not imp safety of the subject or the interpretation of the trial results. The medical monitor should be contacted to discuss individual cases, as needed. Criteria are provided in Section 3.7.3.2. In addition, subjects with the following laboratory test and ECG results at screening must be expressed from the trial:         
 
Platelets ≤ 75000/mm³
 
Hemoglobin ≤ 9 g/dL
 
Neutrophils, absolute ≤ 1000/mm³
 
AST > 2 × ULN
 
ALT > 2 × ULN
 
CPK > 3 × ULN, unless discussed with and approved by the medical monitor
 
Creatinine ≥ 2 mg/dL
 
QTeF ≥ 450 msec in men and ≥ 470 msec in women, unless due to ventricular pacing.
 
 
 
Tests with exclusionary results should be repeated to ensure reproducibility of the abnormal before excluding a subject based on the criteria noted above. For ECG, perform 3 consecutive recordings. If 2 of the 3 remain exclusionary then the subject must be excluded.
 
Subjects with a positive drug screen for cocaine or other drugs of abuse (excluding stimular other prescribed medications and marijuana) are excluded and may not be retested or rescresubjects with a positive urine drug screen resulting from use of prescription or OTC medical products that in the investigator's documented opinion do not signal a clinical condition that impact the safety of the subject or interpretation of the trial results may continue evaluation trial following consultation and approval by the medical monitor.
 
Subjects with a history of a gastric bypass surgery that creates a malabsorptive state, including Roux-en-Y gastric bypass and biliopancreatic bypass with duodenal switch. This does not in gastric banding, gastric stap

	

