# Table 3.4.3-1 Exclusion Criteria Rollover Subjects from Trial 331-201-00080 or 331-201-00081 30. Subjects with a major protocol violation during the course of their participation in the double-blind phase 3 trial (ie, Trial 331-201-00080 or 331-201-00081). Minor violations such as occasional visits outside of the acceptable window or a missing blood draw will not exclude a subject from participation in Trial 331-201-00083; however, continual lack of compliance with the visit schedule, trial assessments, or treatment regimen in the prior double-blind trial would be considered a major violation that would result in exclusion from Trial 331-201-00083. The medical monitor should be contacted if the investigator is unsure of a subject's eligibility.

AE = adverse event; ALT = alanine aminotransferase; AST = aspartate aminotransferase; BMI = body mass index; CPK = creatine phosphokinase; C-SSRS = Columbia-Suicide Severity Rating Scale; DBP = diastolic blood pressure; ECG = electrocardiogram; HbA1c = glycosylated hemoglobin; HIV = human immunodeficiency virus; IDDM = insulin dependent diabetes mellitus; OTC = over-the-counter; QTcF = QT interval as corrected by Fridericia's formula; SBP = systolic blood pressure; T4 = free thyroxine; ULN = upper limit of normal; WOCBP = women of childbearing potential.

Nonchildbearing potential is defined as male and female subjects who are surgically sterile (ie, male subjects who have undergone bilateral orchidectomy and female subjects who have undergone bilateral oophorectomy and/or hysterectomy) and female subjects who have been postmenopausal for at least 12 consecutive months.

Subjects must agree to restrictions to medications and lifestyle as described in Section 4.

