<sup>dInformed consent for Trial 331-201-00083 will occur at screening/baseline for rollover subjects and must be obtained before any trial-related procedures specific to the open-label trial are performed.

<sup>eUpdate, if necessary, for rollover subjects.

<sup>fScreening/baseline value will be obtained from the Day 21 (Week 3) visit of Trial 331-201-00080 or Trial 331-201-00081.

Until the information herein is released by Otsuka to the public domain, the contents of this document are Otsuka confidential information and should not be duplicated

<sup>nA urine drug screen and a blood alcohol test are required at the designated times, but either or both can be conducted at any time during the trial at the discretion of the investigator. If results of either or both are positive, the investigator must contact the medical monitor to discuss the subject's eligibility for continued participation in the trial.

OAll positive urine pregnancy test results must be confirmed by a serum test. Subjects with positive urine and serum pregnancy test results at screening, baseline, or screening/baseline must not be enrolled in Trial 331-201-00083. Subjects with positive urine and serum pregnancy test results during the trial must discontinue treatment and be withdrawn from the trial. Pregnancy tests can be performed at any point during the trial if pregnancy is suspected.

<sup>qAE recording will begin with the signing of the ICF for Trial 331-201-00083.

<sup>rAdjustments to the dose of brexpiprazole can be made at scheduled and unscheduled visits during the 26-week open-label treatment phase (ie, Phase B) to optimize efficacy and tolerability as described in the protocol. Subjects must return to the clinic for unscheduled visits if dose adjustments for brexpiprazole are required between scheduled visits.

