hBlood samples for clinical laboratory tests must be drawn after a minimum 8-hour fast at screening and Conversion Week 4, if at all possible. If fasting blood samples are not feasible at screening, nonfasting blood samples may be obtained initially for determining eligibility for the trial. Vital sign and ECG assessments should be completed before any blood samples are collected.

iSee Section 3.4.3 for exclusions based on screening laboratory results.

jA urine drug screen and a blood alcohol test are required at the designated times, but either or both can be conducted at any time during the trial at the discretion of the investigator. If results of either or both are positive, the investigator must contact the medical monitor to discuss the subject's eligibility for continued participation in the trial.

kAll positive urine pregnancy test results must be confirmed by a serum test. Subjects with positive urine and serum pregnancy test results at screening must not be enrolled. Subjects with positive urine and serum pregnancy test results during the trial must discontinue treatment and be withdrawn from the trial. Pregnancy tests can be performed at any point during the trial if pregnancy is suspected.

Confidential - Proprietary Information

41

<sup>mAE recording will begin with the signing of the ICF.

<sup>nAll prescription and non-prescription medications taken during the trial will be recorded as concomitant medications. Details of prohibited and restricted medications are provided in Section 4.1.

<sup>oCross-titration will occur over a 4-week period in order to bring about a stable transition from previous antipsychotic treatment(s) to oral brexpiprazole.

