#### 3.7.3.2 **Clinical Laboratory Assessments**

A central laboratory designated by the sponsor will be used for all laboratory testing required during the trial. The central laboratory should be used for all laboratory testing whenever possible (including unscheduled and follow-up, if needed). In cases where an immediate result is required for a particular laboratory test, the sample should be divided and sent to both a local laboratory and the designated central laboratory. Subjects should be fasting for a minimum of 8 hours prior to the blood draws, if possible. If fasting blood samples are not feasible at screening, nonfasting blood samples may be obtained initially for determining eligibility for the trial. The results of these tests at screening must be

54

Confidential - Proprietary Information

reviewed by the investigator prior to initiation of the administration of the IMP. Additional urine and blood samples may be collected for further evaluation of safety as warranted by the investigator's judgment. Reports from the central laboratory should be filed with the source documents for each subject. The central laboratory will provide

laboratory results to the sponsor electronically.

Table 3.7.3.2-1 Clinical Laboratory	Assessments
Hematology:	Serum Chemistry:
White Blood Cell (WBC) count with differential	Alkaline Phosphatase (ALP)
Red Blood Cell (RBC) count	Alanine Aminotransferase (ALT)
Hematocrit	Albumin
Hemoglobin	Aspartate Aminotransferase (AST)
Platelet count	Bicarbonate
	Bilirubin, total
Urinalysis:	Blood Urea Nitrogen (BUN)
pH	Creatine phosphokinase (CPK)
Specific Gravity	Calcium
Protein	Chloride
Ketones	Cholesterol (total, low density lipoprotein, and high
Glucose	density lipoprotein)
Blood	Creatinine
Microscopic analysis (performed only if any part of	Gamma Glutamyl Transferase (GGT)
the urinalysis is not negative)	Glucose
	HbA1c
Urine Drug Screen:	Inorganic phosphorus
Amphetamines	Insulin
Barbiturates	Lactic Dehydrogenase (LDH)
Benzodiazepines	Magnesium
Cannabinoids	Potassium
Cocaine	Prolactin
Marijuana	Protein, total
Methadone	Sodium
Opiates	Thyroid Stimulating Hormone (TSH)
Phencyclidine	Thyroxine, Free (T 4 ) (if needed)
Propoxyphene	Uric acid
1 21	Triglycerides
Other:	Trigrycerides
Blood Alcohol	Additional Tests:
	Urine or serum pregnancy for WOCBP
	Prothrombin time (PT)
	Activated partial thromboplastin time (aPTT)
	International normalized ratio (INR)
	HbA1c
	Additional Tests (screening only);
	HIV
	HbsAg

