	anti-HCV
ALP = alkaline phosphatase; BUN = blood urea nitrog	

ALP = alkaline phosphatase; BUN = blood urea nitrogen; GGT = gamma glutamyl transferase; LDH = lactic dehydrogenase; MCHC = mean corpuscular hemoglobin concentration; RBC = red blood cell; WBC = white blood cell.

Confidential - Proprietary Information

55

Any value outside the normal range will be flagged for the attention of the investigator who must indicate whether or not a flagged value is of clinical significance. If one or more values are questionable, the test(s) may be repeated. If the result of any test (or repeat test, if done) is indicated as clinically significant in the samples taken during the screening period, the subject will NOT be enrolled into the trial without the permission of the medical monitor. In addition, follow-up unscheduled laboratory tests should be performed if clinically significant abnormalities are observed. Unscheduled laboratory tests may be repeated at any time at the discretion of the investigator for appropriate medical care. Refer to Appendix 5 for criteria for identifying values of potential clinical relevance.

The following laboratory test results at screening are exclusionary:

- Platelets  $\leq 75000/\text{mm}^3$
- Hemoglobin  $\leq 9 \text{ g/dL}$
- Neutrophils, absolute ≤ 1000/mm^3
- Aspartate aminotransferase (AST)  $> 2 \times$  upper limit of normal (ULN)
- Alanine aminotransferase (ALT) > 2 × ULN
- Creatine phosphokinase (CPK) > 3 × ULN, unless discussed with and approved by the medical monitor
- Creatinine  $\geq 2 \text{ mg/dL}$

The total volume of blood to be collected during the trial is expected to be approximately 50 mL.

A pregnancy test will be conducted in WOCBP prior to trial intervention; results must be available prior to the administration of the IMP. Pregnancy tests can be performed at any point during the trial if pregnancy is suspected.

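### In SAP Appendix 2, 25 of 29 laboratory tests are flagged on an absolute limit with no baseline condition, so an abnormality carried over from the parent trial counts as an open-label finding

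*Protocol*

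**What the plan says.** **Analysis.** SAP Section 9.2 plans means and mean changes from baseline for laboratory tests. It also plans a summary and listing of values in the open-label phase that meet the Appendix 2 criteria. SAP Section 9 presents safety summaries by parent-study treatment group and overall.

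**Baseline.** SAP Section 7.1 takes the last value before the first open-label dose. For rollovers, Protocol Table 3.7-1 footnote f fixes the source: "Screening/baseline value will be obtained from the Day 21 (Week 3) visit of Trial 331-201-00080 or Trial 331-201-00081". Protocol Section 3.2.2.1 says the first open-label dose "will be taken one day after the last dose of double-blind IMP is taken" in the parent trial. SAP Sections 3.1 and 6 state that no de novo subjects were enrolled, so this describes everyone.

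**Criteria.** Appendix 2 conditions on baseline for hematocrit (a fall of at least 3 percentage points) and for three urinalysis items (a rise of at least 2 units). Its other tests have an absolute limit only. Appendices 1 and 3 carry a footnote requiring both the limit and a stated change from baseline, and most of their rows give such a change. The QTc new-onset categories in SAP Section 9.4 require that the value was not reached at baseline. The lipid and glucose table in SAP Section 9.2.2 is also conditioned on baseline.

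**Entry limits.** Protocol Section 3.7.3.2 introduces seven limits with "The following laboratory test results at screening are exclusionary" and names no subject type. Criterion 18 of Table 3.4.3-1, under the de novo heading, gives the same seven and refers back: "Criteria are provided in Section 3.7.3.2".

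**The concern.** An incidence of flagged values in the open-label phase will be read as what happened on open-label brexpiprazole. For 25 of the 29 tests the visible criteria cannot support that reading. A subject with prolactin above the ULN at Day 21 and again at Week 12 counts the same as one whose prolactin first rose at Week 12. A man with hemoglobin of 10 g/dL at both times also counts, because Appendix 2 flags men at 11.5 g/dL or below.

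The point has extra weight in an extension trial. Subjects who had brexpiprazole in the parent trial reach baseline after 3 weeks of drug, so a Day 21 abnormality may itself be a drug effect; in other subjects it may not. A single pooled count per arm mixes carried-over with new findings. The SAP conditions vital signs, most ECG findings, QTc, lipids and glucose on baseline, so the laboratory-relevance table is the exception to its own practice.

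**Working it through.** The plan states no figure to reproduce here. The check is a count, followed by a range under labelled assumptions.

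**1. Count of Appendix 2**, taking sex-specific limits as one test and fasting and non-fasting glucose as one test:
- chemistry 10: AST, ALT, ALP, LDH, BUN, creatinine, uric acid, bilirubin, CPK, prolactin
- hematology 7: hematocrit, hemoglobin, WBC, eosinophils, neutrophil percentage, absolute neutrophils, platelets
- urinalysis 3: protein, glucose, casts
- additional 9: chloride, potassium, sodium, calcium, glucose, total cholesterol, LDL, HDL, triglycerides

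Total 10 + 7 + 3 + 9 = 29. Relative to baseline: 4 (hematocrit and the three urinalysis items). Absolute limit only: 29 − 4 = 25.

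Other counting rules give a similar picture: 26 of 30 if glucose is split by fasting state; 29 of 34 if all sub-rows are split; 35 of 40 if high and low directions are split too.

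**2. Tests summarised against baseline elsewhere.** SAP Section 9.2.2 covers LDL, HDL, triglycerides and fasting glucose: 25 − 4 = 21 tests with no visible baseline-conditioned incidence summary, setting aside the combined liver-injury table in Section 9.2.1. Crediting all four is generous. Section 9.2.2 uses 126 mg/dL for high glucose and 40 mg/dL for low HDL in both sexes, against 100 mg/dL fasting and 50 mg/dL in women in Appendix 2.

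**3. Would the entry limits remove the problem if they bound rollovers?**

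| Test | Entry limit (3.7.3.2) | Appendix 2 limit | Baseline hit still possible? |
|---|---|---|---|
| AST, ALT | > 2 × ULN | ≥ 3 × ULN | No |
| Creatinine | ≥ 2 mg/dL | ≥ 2.0 mg/dL | No |
| Absolute neutrophils | ≤ 1000/mm³ | ≤ 1,000/mm³ | No |
| CPK | > 3 × ULN unless approved | ≥ 3 × ULN | Only by approval or at exactly 3 × ULN |
| Hemoglobin | ≤ 9 g/dL | ≤ 11.5 men, ≤ 9.5 women | Yes, above 9 |
| Platelets | ≤ 75,000/mm³ | ≤ 75,000 or ≥ 700,000/mm³ | Yes, high side |

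Four tests are fully blocked. They do not overlap with the four in step 2, so on the reading kindest to the plan 25 − 4 − 4 = 17 tests have neither protection, or 16 if CPK is treated as blocked.

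**4. Size.** Carried-over subjects per test = N × b × p, where b is the proportion meeting the criterion at baseline and p the proportion of those who still meet it later. N = 384 is the protocol's estimate of rollovers. The documents give neither b nor p, so the values below are assumptions.
- b = 0: 0 subjects
- b = 0.01: 384 × 0.01 × 0.5 = 1.9 to 384 × 0.01 × 1 = 3.8
- b = 0.10: 384 × 0.10 × 0.5 = 19.2 to 384 × 0.10 × 1 = 38.4

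The part of a reported incidence that is carry-over is b × p: nil at b = 0, and up to 10 percentage points at b = 0.10, p = 1.

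**The case against.** **The plan may already deal with this out of sight.** The content of SAP Sections 5.2, 10 (conventions) and 12 (list of tables) is redacted or not shown. A baseline convention or a shift table could sit there. This stands, and it limits the finding to what the visible criteria do.

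**The table is not called treatment-emergent.** It reports values of potential clinical relevance, and mean changes, listings and summaries by parent-study arm are also planned. These reduce the harm: anyone can trace a flagged subject's baseline by hand. They do not give an incidence of new abnormality.

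**A reader might infer more about entry:** that rollovers come in with no laboratory check, or that sites would apply different rules, because Section 3.7.3.2 names no subject type and the only rollover exclusion is criterion 30 ("Subjects with a major protocol violation during the course of their participation in the double-blind"). The documents do not support that. Criterion 18 sits under the de novo heading, and the schedule footnote "See Section 3.4.3 for exclusions based on screening laboratory results" appears only on the de novo schedule. For a screening result marked clinically significant, Section 3.7.3.2 says "the subject will NOT be enrolled into the trial without the permission of the medical monitor", with no limit to one subject type. What remains is a wording clarification.

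**A reader might also infer a gap for late results,** since "A central laboratory designated by the sponsor will be used for all laboratory testing required during the trial" and dosing is expected the day after Day 21. But Section 3.7.3.2 requires review of screening results before dosing and allows a divided sample to a local laboratory when an immediate result is needed. Section 3.13 provides a joint investigator and sponsor decision for a subject enrolled against eligibility criteria. The step is largely covered.

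**Conclusion.** The counting point holds on the visible text and is minor. Of 29 Appendix 2 tests, 25 count a persisting Day 21 abnormality as an open-label finding, and 21 of those have no visible baseline-conditioned incidence summary. This is true whether or not the entry limits apply to rollovers.

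The number of subjects affected is unknown. The 0 to 38.4 per test rests on assumed values of b and p and on an enrolment estimate of 384. It would be tempting to assume a near-zero effect for the seven tests with an entry limit. That is not safe for hemoglobin and platelets, whose Appendix 2 limits are wider than the entry limits.

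The primary endpoint, frequency and severity of adverse events, is not affected. If a redacted convention already restricts or splits the counts by baseline status, only a cross-reference is missing.

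**What to change.** In SAP Section 9.2, report Appendix 2 incidence split by whether the baseline value met the same criterion:
- take treatment-emergent incidence from subjects who did not meet it at baseline;
- list those who did, with baseline and worst on-treatment values, so that worsening stays visible;
- show both by parent-study treatment group and overall, as Section 9 already plans.

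The cost is one table split with no new visits, tests or data. Denominators for the treatment-emergent rows fall to 384 × (1 − b): 380.2 at b = 0.01 and 345.6 at b = 0.10. If SAP Section 10 already has such a rule, cite it in Section 9.2 instead.

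If the protocol is revised for another reason, a phrase in Section 3.7.3.2 saying which subjects the seven limits apply to would remove the ambiguity. It does not need an amendment of its own.

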## 3.7.3.3 Physical Examination and Vital Signs

## 3.7.3.3.1 Physical Examination

A complete physical examination will consist of measurement of height and waist circumference and a review of the following body systems: head, eyes, ears, nose, and throat; thorax; abdomen; urogenital; extremities; neurological; and skin and mucosae. Height will be measured with a stadiometer, measuring stick, or tape. Waist circumference will be measured with each physical examination. The following procedures will aid in the standardization of these measurements:

• The subject should be minimally clothed (ie, lightweight clothing; no heavy overgarments).

- Waist circumference should be recorded before a subject's meal and at approximately the same time at each visit.
- The waist circumference measurement will be accomplished by locating the upper hip bone and the top of the right iliac crest and placing a weighted measuring tape in a horizontal plane around the abdomen at the level of the crest. Before reading the tape measure, the assessor should assure that the tape is snug, but does not compress the skin, and is parallel to the floor. The measurement is to be made at the end of a normal exhalation. 

The principal investigator or his/her appointed designee is primarily responsible to perform the physical examination. If the appointed designee is to perform the physical examination, he/she must be permitted by local regulations and his/her name must be included on the Food and Drug Administration (FDA) Form 1572. Whenever possible, the same individual should perform all physical examinations. Any condition present at the post-treatment physical examination that was not present at the baseline examination should be documented as an AE and followed to a satisfactory conclusion.

